9.7.1.6.2 SECONDARY EFFICACY ANALYSES

Analyses for Key Secondary Efficacy Endpoints (revised per Amendment 06):

The key secondary analyses will be performed only if the primary analysis is significant. The treatment effect for elenbecestat 50 mg/day versus placebo, for each key secondary efficacy endpoint, will be tested using a sequential testing procedure at a significance level of 2-sided alpha = 0.05, ie, any test will start only if the test with higher hierarchical order is significant.

The change from baseline in ADCOMS at 24 months will be analyzed using the same MMRM model as the primary efficacy analysis to compare elenbecestat 50 mg per day versus placebo on the FAS, using baseline ADCOMS in the model.

The change from baseline in amyloid PET SUVR at 24 months will be analyzed using the same MMRM model as the primary efficacy analysis to compare elenbecestat 50 mg per day versus placebo on the FAS, using baseline amyloid PET SUVR in the model. The same analysis will be performed within study as key secondary efficacy endpoint analyses.

Analyses for Other Secondary Endpoints (revised per Amendment 06)

The change from baseline in CDR-SB and ADCOMS at 24 months will be analyzed using the same MMRM model as the primary analysis for subjects enriched by baseline PET SUVR between e.g. 1.2 and 1.6 on the FAS.

The rate of change over time (mean slope) based on change from baseline in the CDR-SB will be analyzed using linear mixed effects (LME) models for multivariate normal data derived from a random coefficient model (slope analysis), where the mean slope in each group depends on a continuous assessment time. The LME model will include treatment group, baseline CDR-SB, randomization stratification variables, assessment time, baseline CDR-SB-by-assessment time, and treatment group-by-assessment time. ApoE4 status may be included in the model if appropriate.

Time to worsening of CDR scores by 24 months will be analyzed on the FAS using Cox regression model for treatment effect adjusting for randomization stratification factors. *ApoE4* status may be included in the model if appropriate. (revised per Amendment 06) Time to worsening of a CDR score is defined as time from randomization to worsening of the CDR score (ie, the first worsening in 2 consecutive scheduled visits). For subjects whose CDR scores have not worsened by the end of the Treatment Period of the Core Study, the time to worsening of the CDR score will be censored at the date of last CDR assessment for these subjects.

Time to conversion to dementia for subjects who were not clinically staged as dementia at Baseline based on clinical diagnosis will be analyzed on the FAS using Cox regression model for treatment effect adjusting for randomization stratification factors. *ApoE4* status may be included in the model if appropriate. (revised per Amendment 06) Proportion of subjects with

dementia diagnosis at 24 months will be estimated using Kaplan—Meier method based on time to conversion to dementia based on clinical diagnosis. Time to conversion to dementia for subjects who were not clinically staged as dementia at Baseline based on clinical diagnosis is defined as time from randomization to conversion to dementia based on clinical diagnosis. For subjects without clinical dementia by the end of study, the time to conversion to dementia based on clinical diagnosis will be censored at the date of last dementia diagnosis.

The other continuous secondary efficacy endpoints as defined above will be analyzed using the same MMRM model as the primary efficacy analysis to compare elenbecestat 50 mg per day versus placebo on the FAS, using baseline value corresponding to the response variable in the model.

The relationship between clinical changes at 24 months (CDR-SB, ADCOMS, ADAS-cog14, MMSE, and FAQ) and changes in each of the biomarkers (amyloid PET, tau PET, CSF A β (1-42), t-tau, p-tau, vMRI, and fMRI) at 24 months, will be evaluated using an ANCOVA model. (revised per Amendments 01, 04, 05, and 06) Changes in clinical scales at 24 months will be the response variables and either continuous or categorical change of biomarkers will be independent variables. The ANCOVA model will also include baseline value for clinical scale as a covariate, with treatment group and randomization stratification variables, as factors. *ApoE4* status may be included in the model if appropriate. (revised per Amendment 06)

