The change from baseline in CDR-SB and ADCOMS at 24 months will be analyzed using the same MMRM model as the primary analysis for subjects enriched by baseline PET SUVR between e.g. 1.2 and 1.6 on the FAS.

The rate of change over time (mean slope) based on change from baseline in the CDR-SB will be analyzed using linear mixed effects (LME) models for multivariate normal data derived from a random coefficient model (slope analysis), where the mean slope in each group depends on a continuous assessment time. The LME model will include treatment group, baseline CDR-SB, randomization stratification variables, assessment time, baseline CDR-SB-by-assessment time, and treatment group-by-assessment time. *ApoE4* status may be included in the model if appropriate.

Time to worsening of CDR scores by 24 months will be analyzed on the FAS using Cox regression model for treatment effect adjusting for randomization stratification factors. *ApoE4* status may be included in the model if appropriate. (revised per Amendment 06) Time to worsening of a CDR score is defined as time from randomization to worsening of the CDR score (ie, the first worsening in 2 consecutive scheduled visits). For subjects whose CDR scores have not worsened by the end of the Treatment Period of the Core Study, the time to worsening of the CDR score will be censored at the date of last CDR assessment for these subjects.

Time to conversion to dementia for subjects who were not clinically staged as dementia at Baseline based on clinical diagnosis will be analyzed on the FAS using Cox regression model for treatment effect adjusting for randomization stratification factors. *ApoE4* status may be included in the model if appropriate. (revised per Amendment 06) Proportion of subjects with dementia diagnosis at 24 months will be estimated using Kaplan–Meier method based on time to conversion to dementia based on clinical diagnosis. Time to conversion to dementia for subjects who were not clinically staged as having dementia at Baseline based on clinical diagnosis is defined as time from randomization to conversion to dementia based on clinical diagnosis. For subjects without clinical dementia by the end of study, the time to conversion to dementia based on clinical diagnosis will be censored at the date of last dementia diagnosis.

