Abnormal laboratory values should not be listed as separate AEs if they are considered to be part of the clinical syndrome that is being reported as an AE. It is the responsibility of the investigator to review all laboratory findings in all subjects and determine if they constitute an AE. Medical and scientific judgment should be exercised in deciding whether an isolated laboratory abnormality should be classified as an AE. Any laboratory abnormality considered to constitute an AE should be reported on the Adverse Event eCRF.

Abnormal ECG (QTc) results, if not otherwise considered part of a clinical symptom that is being reported as an AE, should be considered an AE if the QTc interval is more than 450 ms and there is an increase of more than 60 ms from baseline. If the QTcF is greater than 450 ms on the first single 12-lead ECG, 2 additional 12-lead ECGs will be performed 1 minute apart and the mean of the 3 QTcF values will be calculated. Any ECG abnormality that the investigator considers as an AE should be reported as such.

Cognitive decline will be assessed as a safety assessment in addition to an efficacy assessment. Cognitive assessments include the CDR, ADAS-cog14, and MMSE (see [Section 9.5.1.3.1](#)). If these assessments show cognitive decline during the Treatment Period, and if this cognitive decline is considered by the investigator to be excessive relative to the subject's recent AD history, this finding should be reported as an AE. It is the responsibility of the investigator to review the cognitive assessments and to determine if any result constitutes an AE.

AEs that may signal drug abuse potential will require a more detailed follow-up through completion of a specific eCRF form. Similarly, AEs reported during the first 4 weeks following the last dose of study drug that might indicate physical dependency also require a more detailed follow-up through completion of the same eCRF form. This includes AEs that fall into the categories listed below. Examples of such AEs are provided in [Appendix 3](#) and a more comprehensive list is provided in the eCRF Completion Guidelines. This additional follow-up of AEs that signal possible drug abuse potential, including physical dependency following discontinuation from study drug, is in line with current FDA Guidance for Industry for "Assessment for Abuse Potential for Drugs" ([FDA 2017 Abuse Potential Guidelines](#)), (revised per Amendment 04)

Euphoria-related terms: (revised per Amendment 04)

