9.7.1.6.3 EXPLORATORY EFFICACY ANALYSES

Time to change of concomitant AD treatment will be analyzed similarly to that for time to conversion to dementia based on clinical diagnosis. Time to change of concomitant AD treatment is defined as time from randomization to the first dose increase and/or initiation of treatment with AChEI or memantine after randomization. For subjects without any change of concomitant AD treatment by the end of study, the time to change of concomitant AD treatment will be censored at the date of last assessment of concomitant medication.

The proportion of subjects with any change of concomitant AD treatment at 24 months will be analyzed similarly to that for proportion of subjects with dementia diagnosis at 24 months.

The rate of change over time (mean slope) based on change from baseline in the NPI-10 item will be analyzed in a manner similar to that used for the rate of change over time (mean slope) based on change from baseline in the CDR-SB.

The analysis of the following exploratory efficacy endpoints will be performed to compare elenbecestat versus placebo using the appropriate prespecified statistical methods including MMRM model, analysis of covariance model (ANCOVA), etc. For each exploratory efficacy endpoint, the treatment effect for elenbecestat 50 mg per day versus placebo will be tested at a significance level of 2-sided alpha = 0.05.

- Change from baseline in NPI-10 item at 24 months

- Change from baseline in EQ-5D (subject self-reported, study partner self-reported, and subject measured by proxy) and QOL-AD (subject and study partner) at 24 months
- Change from baseline in Zarit's Burden Interview at 24 months

Additional analyses may be performed as needed.

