9.7.2 Determination of Sample Size

The sample size for this study is estimated for comparison of elenbecestat versus placebo with respect to a pooled analysis of studies E2609-G000-301 and E2609-G000-302 for the change from baseline in CDR-SB at 24 months. Based on the available data from the placebo group in Study BAN2401-G000-201 (a recently completed study with a comparable subject population), the mean and the standard deviation of the change from baseline in CDR-SB at 24 months in the placebo group are assumed to be 1.46 and 2.05, respectively, instead of 1.75 and 2.05, which are originally assumed by the available data from ADNI (of amyloid positive, MMSE equal or greater than 24, late MCI [global CDR=0.5, CDR memory box \geq 0.5]). Therefore, assuming a 25% reduction in the mean change from baseline CDR-SB at 24 months for elenbecestat compared to placebo with common standard deviation of 2.05 and 30% dropout rate, a total sample size of 1900 subjects, 950 subjects in each treatment group, will be required to detect the treatment difference between elenbecestat and placebo using a 2-sample t test with 90% power at a significance level of 2 sided alpha =0.05.

The pooled data from 2 studies (E2609-G000-301 and E2609-G000-302) will comprise the total sample size of approximately 1900 subjects. At least 850 subjects will be randomized in each study. (revised per Amendment 06)

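### The CDR-SB slope model lets the randomization strata shift the level of change but not its slope, so the slope comparison is modestly less precise than the stratified design allows

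*Protocol*

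**What the plan says.** Section 9.7.1.6.2 takes change from baseline as the response: "The rate of change over time (mean slope) based on change from baseline in the CDR-SB will be analyzed". The model is a linear mixed model "derived from a random coefficient model (slope analysis), where the mean slope in each group depends on a continuous assessment time". Its fixed effects are listed in full: "The LME model will include treatment group, baseline CDR-SB, randomization stratification variables, assessment time, baseline CDR-SB-by-assessment time, and treatment group-by-assessment time". The synopsis, under the analyses for other secondary endpoints, gives the same list, beginning "The LME model will include treatment group, baseline CDR-SB, randomization stratification variables, assessment time". *ApoE4* status is the only optional addition.

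Section 9.7.1.6.3 carries the form to a second endpoint: the mean slope "based on change from baseline in the NPI-10 item will be analyzed in a manner similar" to the CDR-SB slope.

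The strata are region (7 levels), clinical dementia staging (at most about 25% with early mild dementia) and concurrent AD-medication use (section 9.1). The slope is an other secondary endpoint, outside the sequential testing of the key secondary endpoints. Section 9.7 sets a two-sided 5% level for all tests unless otherwise specified.

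**The concern.** In this model the treatment effect is the treatment-by-time coefficient. A covariate sharpens that coefficient only if it is allowed to predict the slope. A main effect adds the same constant at every visit, so it can explain why one stratum sits higher than another but not why it declines faster. The authors gave baseline CDR-SB a time interaction and gave the randomization factors none.

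The primary MMRM in section 9.7.1.6.1 also enters the strata as main effects, but its contrast is a level at Month 24, which a main effect does adjust. The same term moved into a slope model no longer does that job. Any difference in decline between strata stays in the random-slope variance and widens the interval for the slope difference. What is at stake is precision on a stated superiority objective, not validity.

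A second feature bears on interpretation. Change from baseline is zero in both arms at randomization, yet the treatment main effect gives each arm its own fitted value there. The slope difference alone therefore does not say where the arms stand at Month 24.

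**Working it through.** **The plan's own figure first.** Section 9.7.2 gives a placebo mean and SD that "in the placebo group are assumed to be 1.46 and 2.05, respectively", a 25% reduction, 30% dropout, and 950 per arm "using a 2-sample t test with 90% power at a significance level of 2 sided alpha =0.05".
- Difference: 0.25 × 1.46 = 0.365.
- Completers per arm: 2 × (1.960 + 1.282)² × 2.05² / 0.365² = 663.
- With dropout: 663 / 0.70 = 948 per arm, 1896 in total, against 1900 stated. It reproduces.
- 950 × 0.70 = 665 completers per arm, used below.

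The protocol states no power or precision for the slope.

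**Slope precision as written.** CDR visits are at Months 3, 6, …, 24. Let u = month/24, so slopes are in points per 24 months. Assumed within-subject covariance of the changes: V = b²·uu′ + s²·J + s²·I, where the J term is the baseline error shared by all changes. V is constrained so that the Month 24 variance is 2.05² = 4.2025, hence b² = 4.2025 − 2s². The protocol gives no variance components, so s² = 0.25 to 1.0 is an assumption. The per-subject slope variance v is the slope element of (X′V⁻¹X)⁻¹ with X = [1, u], and SE = √(2v/665).
- s² = 0.25: v = 4.08, SE = 0.111.
- s² = 1.0: v = 3.73, SE = 0.106.

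**What a dementia-by-time term would remove.** If a share p = 0.25 declines g points faster over 24 months, the between-stratum slope variance is B = p(1 − p)g², and the written SE is too wide by the factor 1/√(1 − B/v).

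| g (assumed) | B | factor, s² = 0.25 | factor, s² = 1.0 |
|---|---|---|---|
| 0.5 | 0.047 | 1.006 | 1.006 |
| 1.0 | 0.188 | 1.024 | 1.026 |
| 1.5 | 0.422 | 1.056 | 1.062 |

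A separate calculation with 950 per arm, 30% monotone dropout and different variance components gives 0.1027 unadjusted against 0.1021, 0.1005 and 0.0977 adjusted. The factors are 1.005, 1.022 and 1.051. Power for a proportional 25% slowing goes from 0.945 to 0.947, 0.953 and 0.962. With a 15% dementia share the factors are 1.004, 1.015 and 1.034.

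None of this subtracts what baseline CDR-SB by time already explains, so the figures are upper values for a given g. Region and AD-medication use are not included.

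**Why the intercept should be reported.** Suppose elenbecestat is 0.30 worse at Month 3 and the gap closes linearly to zero at Month 24 (an assumed pattern).
- Fitted slope difference: −0.30 × 24/21 = −0.343, or 0.343/1.46 = 23.5% slowing.
- z = −0.343/0.111 to −0.343/0.106, about −3.1 to −3.2. Without the shared baseline error in V, it is about −2.9 to −3.0.
- Fitted intercept difference: +0.343. Fitted Month 24 difference: 0.343 − 0.343 = 0.

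The last line is what keeps the slope from being misread.

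**Why the treatment main effect should stay.** Suppose instead elenbecestat is a constant 0.30 better at every visit, with equal rates of decline. The written model returns a slope difference of 0, which is right for a rate. With the main effect removed, the same data give −0.16 (11% slowing, z −1.5 to −1.6), or −0.42 (29%, z −3.9 to −4.1) if V has no shared baseline error.

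**The case against.** The strongest reply is that this is a modelling preference. The strata are in the model, the primary MMRM has the same form, the loss is at most a few percent of an SE, and it depends on a difference in decline that no document gives. Eligibility is narrow (global CDR 0.5, MMSE at least 24), and baseline CDR-SB by time may already capture much of what dementia staging would predict. All of that limits the size, and it stands. It does not answer the structural point: a main effect that adjusts a Month 24 level does not adjust a slope.

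A reader might go further and infer that the treatment main effect is itself an error, and that the model can declare slowing for a drug with no benefit. The arithmetic for an early deficit that closes is correct, but the documents do not support the inference, for four reasons.
- With no difference at any visit, the test keeps its 5% level. The apparent slowing needs an early deficit that later closes. The statement "Cognitive decline will be assessed as a safety assessment in addition to an efficacy assessment" in section 9.5.1.5.1 provides for monitoring; it does not predict that pattern.
- The primary analysis estimates the Month 24 difference directly, with a confidence interval, and would show no benefit in that case.
- Removing the main effect pushes a pure level shift into the slope. The programme wants to separate symptomatic effects from disease modification: the 27-month CDR-SB objective was added for that purpose (revision history, Amendment 01).
- A common intercept does not fully cure the example. Under the covariance with shared baseline error it still shows 11% slowing (z −1.5 to −1.6).

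**Conclusion.** The concern holds as a modest loss of precision. The slope model in section 9.7.1.6.2 and the synopsis does not adjust treatment by time for the randomization strata. The SE of the slope difference is about 0.5% to 6% too wide if the dementia stratum holds 25% of subjects and declines 0.5 to 1.5 points faster over 24 months. Both the gap and the variance components are assumptions. The loss is smaller where baseline CDR-SB by time already accounts for the gap, or where the stratum is smaller.

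Arm-specific intercepts are a defensible choice with a known trade-off. They call for fuller reporting, not for removal. The slope test's type I error is intact when the arms do not differ, and the primary MMRM conclusion is untouched.

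**What to change.** In section 9.7.1.6.2 and the matching synopsis paragraph, add randomization stratification variables by assessment time to the slope model. State in section 9.7.1.6.3 that the NPI-10 slope uses the same form.

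Keep the treatment main effect. Add one sentence requiring the fitted between-arm intercept difference and the model-implied Month 24 difference to be reported, with confidence intervals, beside the slope difference.

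The cost is a sentence or two of text and a few more fixed effects (six for region, one each for dementia staging and AD-medication use) in about 1900 subjects. No new data are needed.

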9.7.1.1.2 SECONDARY ENDPOINTS

The key secondary endpoints of the study are as follows (revised per Amendment 06):

- Change from baseline in ADCOMS at 24 months in the combined studies
- Change from baseline in amyloid PET SUVR at 24 months for brain amyloid levels in the combined studies
- Change from baseline in amyloid PET SUVR at 24 months for brain amyloid levels in the individual studies

The other secondary endpoints of the study are as follows (revised per Amendment 06):

- Change from baseline in the CDR-SB at 24 months for subjects enriched by baseline PET SUVR, eg, between 1.2 and 1.6, in the combined studies
- Change from baseline in the ADCOMS at 24 months for subjects enriched by baseline PET SUVR, eg, between 1.2 and 1.6, in the combined studies
- The rate of change over time (mean slope) based on CDR-SB score over 24 months in the combined studies
- Time to worsening of CDR scores by 24 months (eg, the worsening of global CDR score is defined as an increase from baseline by at least 0.5 points on the global CDR scale on 2 consecutive scheduled visits at which global CDR is undertaken) in the combined studies
- Time to conversion to dementia by 24 months for subjects who were not clinically staged as dementia at Baseline based on clinical diagnosis in the combined studies (revised per Amendment 01)
- Change from baseline in CDR-SB at 27 months (ie, 24 months of treatment plus 3 months posttreatment follow-up) in the combined studies (revised per Amendment 01)
- Change from baseline in ADAS-cog14, MMSE, and FAQ at 24 months in the combined studies
- Change from baseline in ADAS-cog14 Word List (immediate recall and delayed recall) at 24 months in the combined studies (revised per Amendment 01)

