9.7.1.6.1 PRIMARY EFFICACY ANALYSIS

The primary analysis will be based on an intent to treat philosophy without regard to adherence to treatment. The primary analysis of the change from baseline in CDR-SB at 24 months will be performed to compare elenbecestat 50 mg per day versus placebo using a linear mixed effects model for repeated measures (MMRM) on the FAS. The MMRM model will include fixed effects of treatment group, visit, treatment group by visit interaction, baseline CDR-SB, baseline CDR-SB by visit interaction, and randomization stratification variables (ie, region [7 levels], clinical dementia [yes, no], and concurrent AD medication use at randomization [Visit 2] [yes, no]). *ApoE4* status may be included in the model if appropriate. (revised per Amendments 01, 02, and 06) An unstructured covariance matrix will be employed to model the covariance of within subject effect; if MMRM fails to converge then a covariance structure with fewer parameters from the following list will be employed according to the prespecified order in the list until the MMRM converges. The list of covariance structure will include Heterogeneous Toeplitz, Toeplitz, Heterogeneous Compound Symmetry, and Compound Symmetry. This primary analysis will include all observed post baseline data of the change from baseline in CDR-SB without imputation of missing values. The treatment effect for elenbecestat versus placebo will be compared at 24 months based on MMRM model. The LS means and difference in LS means between elenbecestat treatment group and placebo, and corresponding 95% CI will be presented.

The null hypothesis is that there is no difference in the mean change from baseline in CDR-SB at 24 months between elenbecestat 50 mg per day and placebo. The corresponding alternative hypothesis is that there is a difference in the mean change from baseline in CDR-SB at 24 months between elenbecestat 50 mg per day and placebo.

The primary analysis will be repeated to minimize the impact of change in concomitant AD medications where efficacy data after initiation of new AD medications and increase of current AD medications will be censored.

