The following sensitivity analysis will be conducted to evaluate the impact of missing data: the primary endpoint will be analyzed using ANCOVA after multiple imputation. The ANCOVA model will include baseline CDR-SB as a covariate, with treatment group and randomization stratification variables as factors. *ApoE4* status may be included in the model if appropriate. Additional sensitivity analyses will be performed to assess the robustness of the missing at randomization assumption in the primary MMRM model. Subgroup analysis (eg, stratification factors and *ApoE4* status) and additional sensitivity analysis for the primary endpoint will be performed as appropriate. (revised per Amendments 01 and 06)

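### The Cox models for time to CDR worsening and time to dementia leave out baseline CDR-SB, which forgoes some efficiency, most clearly for time to dementia

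*Protocol*

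**What the plan says.** Section 9.7.1.6.2 gives the same model for both time-to-event secondary endpoints: each is "analyzed on the FAS using Cox regression model for treatment effect adjusting for randomization stratification factors". The only further term is ApoE4, which "status may be included in the model if appropriate". The synopsis repeats this (for CDR worsening: "Time to worsening of CDR scores by 24 months will be analyzed on the FAS using Cox regression model for treatment effect").

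The models whose response is CDR-SB change do carry the baseline score. The primary MMRM in section 9.7.1.6.1 lists "baseline CDR-SB, baseline CDR-SB by visit interaction, and randomization stratification variables". For the multiple-imputation sensitivity analysis, "The ANCOVA model will include baseline CDR-SB as a covariate". For the slope analysis, "The LME model will include treatment group, baseline CDR-SB, randomization stratification variables, assessment time".

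The worsening event is illustrated in section 9.7.1.1.2 as "an increase from baseline by at least 0.5 points on the global CDR scale on 2 consecutive scheduled visits". Both Cox endpoints are listed there as other secondary endpoints, outside the key secondary testing sequence.

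**The concern.** Every subject enters with a global CDR of 0.5 at Screening (section 9.3.1). The baseline value of the global scale therefore says almost nothing about how close a subject is to the next stage. CDR-SB comes from the same six domains (section 9.2.1) and can separate these subjects. It is the obvious candidate for a prognostic baseline term.

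A Cox model that omits a prognostic covariate gives a hazard ratio nearer 1 than the covariate-conditional one whenever a treatment effect exists, and has less power, even under randomization. These are the two secondary endpoints that express progression as time to an event. Only the CDR-SB comparison was powered (section 9.7.2), so these endpoints get whatever precision the model allows.

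**Working it through.** **1. The plan's own figure.** Section 9.7.2 assumes a placebo mean change of 1.46, a 25% reduction, SD 2.05, 30% dropout, 90% power and two-sided 5%.

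- Difference: 0.25 × 1.46 = 0.365.
- Per arm: 2 × (1.960 + 1.282)² × 2.05² / 0.365² = 663.
- With dropout: 663 / 0.7 = 948 per arm, or 1,896 in total against the stated 1,900. It reproduces.

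No hazard ratio, event count or power is stated for either Cox endpoint, so there is no figure of the plan's to recompute for them.

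**2. Is the covariate available?** The CDR is done at Visit 2 before the first dose (section 9.1.2.1). FAS membership requires a baseline primary efficacy measurement (section 9.7.1.2). Adding baseline CDR-SB loses no FAS subject.

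**3. What severity information do the strata carry?** The factors are region, clinical dementia (yes/no) and concurrent AD medication use.

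- *CDR worsening:* all FAS subjects are analyzed, so the dementia factor varies and acts as a coarse severity term.
- *Time to dementia:* only subjects not staged as demented at Baseline are analyzed. Table 4 places staging at Screening, and Table 5 does not repeat it until Visit 6. Baseline staging is therefore the Screening staging and, apart from stratification errors, the factor is constant. Region, medication use and optional ApoE4 remain, with no severity score.

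**4. Size of the effect of omission.** Event times were simulated from hazard = h₀ × exp(θA + γX), where A is treatment and X is a standardized baseline covariate. Cox models were then fitted with and without X. X stands for the part of baseline CDR-SB not explained by the strata; the strata themselves were not simulated.

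Assumed inputs, none given in the protocol for these endpoints unless noted:

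- True conditional treatment hazard ratio exp(θ) = 0.75.
- 24-month control event rate of 30% or 50%.
- 30% dropout (the rate in section 9.7.2).
- N = 1,900 for CDR worsening. N = 0.75 × 1,900 = 1,425 for dementia, from the cap of about 25% with mild dementia.
- exp(γ) from 1.2 to 2.5 per SD.
- Continuous event times; 600 runs per setting.

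Power in %, without → with the covariate:

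| Covariate HR per SD | Treatment HR without / with (range over settings) | CDR worsening, 30% | CDR worsening, 50% | Dementia, 30% | Dementia, 50% |
|---|---|---|---|---|---|
| 1.2 | 0.748–0.756 / 0.747–0.755 | 85.2 → 85.7 | 97.3 → 97.7 | 73.0 → 73.7 | 90.5 → 90.5 |
| 1.5 | 0.751–0.764 / 0.747–0.755 | 83.2 → 84.5 | 95.3 → 97.0 | 73.2 → 74.2 | 90.3 → 93.2 |
| 2.0 | 0.764–0.774 / 0.746–0.751 | 80.7 → 84.8 | 94.5 → 98.3 | 66.7 → 73.5 | 86.3 → 90.8 |
| 2.5 | 0.776–0.791 / 0.745–0.754 | 75.2 → 83.5 | 89.0 → 98.0 | 64.2 → 72.8 | 81.0 → 95.2 |

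The gains by row are 0.0–0.7, 1.0–2.9, 3.8–6.8 and 8.3–14.2 points. The Monte Carlo standard error of one power figure near 80% is √(0.8 × 0.2 / 600) = 1.6 points; the paired differences are more precise.

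The figures also move with the other assumptions. For dementia alone, with a true hazard ratio of 0.75 to 0.80, 35% or 50% conversion and 500 runs per setting, the gain was 6 to 13 points at 2.0 per SD and 12 to 17 at 2.5.

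**5. Under no treatment effect** (N = 1,900, 50% events, 1,500 runs), the model without X gave mean hazard ratios of 0.998 and 1.002 at 1.5 and 2.5 per SD. It rejected in 5.1% and 4.5% of runs.

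**The case against.** A reader might infer that the two hazard ratios are biased and the tests unsound. The simulation does not support that: type I error is nominal and there is no shift under the null. A hazard ratio adjusted only for the strata is a legitimate, less conditional estimand. Reporting about 0.77 where the conditional value is 0.75 mostly reflects two different parameters. This part of the objection stands.

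A reader might also infer that the protocol breaks its own rule. It does not. Its continuous models adjust for the baseline of their own response, and CDR-SB is the response in neither Cox model: one event is illustrated on the global CDR and the other is a clinical diagnosis. Adjusting for the stratification factors follows the randomization, so the choice has a rationale. What remains is that the matching baseline for the worsening event, the global CDR, is nearly constant by the entry criterion, which leaves CDR-SB as the informative substitute.

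Three further points count against giving this much weight. The size depends on an unknown prognostic strength and is negligible at the low end. Both endpoints sit outside the formal hierarchy. Extra covariates for such endpoints are often settled in a statistical analysis plan, which is not at hand. On the last, the protocol does name the adjustment set, and even an optional extra term, so the set is open to comment here.

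**Conclusion.** The point holds as a missed efficiency gain, not as an error. Both Cox models omit a baseline score that every analyzed subject has. If that score predicts the event beyond the strata and the drug works, the reported hazard ratio will lie nearer 1 than the conditional one and power will be lower. The loss is trivial for a weak association and reaches roughly 8 to 14 points only for a strong one (2.5 per SD) in the main set of assumptions. The protocol does not allow one figure to be chosen.

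The case is strongest for time to dementia, where the design leaves no severity term. It is weaker for CDR worsening, where the dementia stratum already absorbs part of the severity signal, so a lower row of the table is the fairer guide. The documents do not support a claim of bias, of an invalid test, or of a known loss for both endpoints.

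**What to change.** In section 9.7.1.6.2 and the matching synopsis text, add baseline CDR-SB as a continuous covariate to both Cox models, alongside the stratification factors, before unblinding. Keep the stratification-only model as a sensitivity analysis.

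The cost is small: a wording change and no new data. The hazard ratio becomes conditional on baseline CDR-SB and should be described that way.

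Removing the clinical-dementia term from the time-to-dementia model is optional tidying, since a constant term changes no result. If it is removed, state that this does not carry over to time to change of concomitant AD treatment. Section 9.7.1.6.3 analyzes that endpoint in the same way as time to dementia, but does not restrict it to non-demented subjects, so the term still varies there. Say at the same place whether baseline CDR-SB enters that model.
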